2.3 Endpoint Analysis

2.3.1 Primary Endpoints (Randomized Cohort)

Primary Effectiveness Endpoint

The primary effectiveness endpoint is the composite endpoint of all-cause mortality or disabling stroke at one year. This endpoint will be evaluated by a non-inferiority test comparing the Portico test group to the control (CAV) group, and the primary analysis will be conducted on the ITT population. The primary analysis will be performed based on combined high and extreme risk cohort with pooled access data.

The primary analysis will be conducted on a dataset locked after all enrolled subjects have had their one-year study visit (except those withdrawn or lost-to-follow-up before one year).

Statistical Analysis Plan

[REDACTED]

[REDACTED]

[REDACTED]

[REDACTED]

[REDACTED]

[REDACTED]

Primary Safety Endpoint

The primary safety endpoint is the non-hierarchical composite endpoint of all-cause mortality, disabling stroke, life-threatening bleeding requiring blood transfusion, acute kidney injury requiring dialysis, or major vascular complications at 30 days. This endpoint will be evaluated by a non-inferiority test comparing Portico test group to the control group, and the primary analysis will be conducted on the ITT population. The primary analysis will be performed based on combined high and extreme risk cohort with pooled access data.

[REDACTED]

Statistical Analysis Plan

[REDACTED]

[REDACTED]

[REDACTED]

[REDACTED]

[REDACTED]

[REDACTED]

[REDACTED]

[REDACTED]

[REDACTED]

[REDACTED]

[REDACTED]

[REDACTED]

[REDACTED]

[REDACTED]

[REDACTED]

[REDACTED]

[REDACTED]

[REDACTED]

[REDACTED]

[REDACTED]

[REDACTED]

[REDACTED]

[REDACTED]

[REDACTED]

Statistical Analysis Plan

[REDACTED]

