#### 1.2.1 Study Design and Objectives (Pivotal IDE)

The PORTICO pivotal IDE trial is a prospective, multi-center, randomized, controlled clinical investigation study designed to evaluate the safety and effectiveness of the SJM Portico Transcatheter Heart Valve and Delivery Systems (Portico) via transfemoral and alternative delivery methods in high-risk and extreme-risk patients.

[figure not shown]
As shown in Figure 1, the pivotal IDE trial includes a randomized cohort of 750 patients that will be used to support a Premarket Approval (PMA) application for the Portico™ Transcatheter Aortic Heart Valve in the United States. Prior to randomization, patients will be classified as high or extreme risk and stratified by vascular access within each risk group. At the time of the primary analysis, the risk cohorts will be combined.

There are two nested-registries within the pivotal IDE trial (Roll-in registry and Valve-in-Valve registry). Data from the IDE Valve-in-Valve registry will be used to support an expanded indication for transcatheter delivery of the Portico valve in a failed surgical bioprosthesis (TAVR-in-SAVR). [REDACTED]

[REDACTED] The objective of the FlexNav study is to characterize the safety of the second-generation Portico Delivery System (“FlexNav™ Delivery System”). Thirty-day outcomes data from the FlexNav study will be used to support the PMA application for the Portico™ Transcatheter Aortic Heart Valve and the FlexNav™ Delivery System. A synopsis of the FlexNav study which includes details such as objectives, endpoints, and other study information is provided in Appendix W.

This protocol conforms to all the standards of Medicare coverage requirements. The PORTICO subject characteristics are consistent with Medicare population and the results are expected to be generalizable to the Medicare population.

Investigators enrolling subjects in the pivotal IDE trial under protocol version L or later will implant the Portico valve using the FlexNav™ Delivery System across all active study arms.

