The objective of this clinical trial is to evaluate the safety and effectiveness of the SJM Portico Transcatheter Heart Valve and Delivery Systems (Portico) via transfemoral and alternative delivery methods. The Portico™ Transcatheter Heart Valve is indicated for patients with symptomatic severe native aortic stenosis, who are considered high or extreme surgical risk. [REDACTED], an additional study arm (“FlexNav study” or “FlexNav cohort”) has been added to the pivotal IDE trial. The objective of the FlexNav study is to characterize the safety of the second-generation Portico Delivery System (“FlexNav™ Delivery System”).

1.3 **Clinical Investigation Design**

The pivotal IDE trial is a prospective, multi-center, randomized, controlled clinical trial, designed to evaluate the safety and effectiveness of the SJM Portico Transcatheter Heart Valve and Delivery Systems (Portico) via transfemoral and alternative delivery methods. The pivotal IDE trial includes a randomized cohort of 750 patients that will be used to support a Premarket Approval (PMA) application for the Portico™ Transcatheter Aortic Heart Valve in the United States. This trial includes both high-risk and extreme-risk patients. Prior to randomization, patients will be classified as high or extreme risk and stratified by vascular access within each risk group. At the time of the primary analysis, the risk cohorts will be combined.

The FlexNav study will be conducted as a prospective, multicenter, investigational study arm of the pivotal IDE trial. Thirty-day outcomes data from the 100 subjects in FlexNav study will be used to support the PMA application for the Portico™ Transcatheter Aortic Heart Valve and the FlexNav™ Delivery System.

1.4 **Endpoints**

1.4.1 **Pivotal IDE Endpoints (Randomized cohort)**

Primary Safety Endpoint

Non-hierarchical composite of all-cause mortality, disabling stroke, life threatening bleeding requiring blood transfusion, acute kidney injury requiring dialysis, or major vascular complications at 30 days.

Primary Effectiveness Endpoint

A composite of all-cause mortality or disabling stroke at one year.

Statistical Analysis Plan

Secondary Endpoints

1. Severe aortic regurgitation (AR) at one year
2. Kansas City Cardiomyopathy Questionnaire (KCCQ) at one year
3. Moderate or severe aortic regurgitation at one year
4. Six-minute walk at one year

Descriptive Endpoints

1. Acute device success defined as:
 - o Absence of procedural mortality AND

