1.5 Randomization (Randomized cohort)

Subjects will be randomized per 1:1 ratio to test (Portico) vs. commercially available valve (CAV). group according to a computer-generated randomization scheme. [REDACTED]

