2.4 Sample Size Calculations (Randomized cohort)

The sample sizes of pivotal IDE trial randomized cohort are estimated based on the primary effectiveness and safety endpoints and tests. The study is powered on combined high and extreme risk cohort. The sample size is calculated to achieve at least 80% power for both primary effectiveness and safety endpoints [REDACTED]

[REDACTED]

[REDACTED]

[REDACTED]

[REDACTED]

[REDACTED]

[REDACTED]

[REDACTED]

Statistical Analysis Plan

[REDACTED]

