2.4.3 Total Sample Size

The total sample size required for evaluating the primary effectiveness and safety endpoints is 750 and 750 subjects respectively. Thus, the total sample size is 750 for the pivotal IDE trial randomized cohort.

[REDACTED]

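### Does pooling the risk cohorts and access routes in the primary analysis throw away the precision of the stratified randomisation?

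*SAP*

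**What the plan says.** On the design, SAP 1.3 states: "Prior to randomization, patients will be classified as high or extreme risk and stratified by vascular access within each risk group". With two risk groups and two access routes this gives four strata, allocated 1:1. Protocol 1.2.1 adds: "At the time of the primary analysis, the risk cohorts will be combined".

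On the analysis, SAP 2.3.1 says of the effectiveness endpoint: "This endpoint will be evaluated by a non-inferiority test comparing the Portico test group to the control (CAV) group", on the ITT population. It says the same in substance for safety. For both endpoints it continues: "The primary analysis will be performed based on combined high and extreme risk cohort with pooled access data".

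On size, SAP 2.4 powers the trial on the two risk cohorts together and states: "The sample size is calculated to achieve at least 80% power for both primary effectiveness and safety endpoints". SAP 2.4.3 gives the result: "The total sample size required for evaluating the primary effectiveness and safety endpoints is 750 and 750 subjects respectively".

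The hypotheses, margin, alpha, test statistic and variance that would follow in SAP 2.3.1 are redacted. So are the details in SAP 1.5 (Randomization), SAP 2.12 (Adjustments for Covariates), Protocol 11.2 (Randomization and Stratification) and the method text of Protocol 11.3.1 and 11.3.2.

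**The concern.** When arms are balanced within strata by design, the variation between strata no longer contributes to the difference between arms. A variance computed as if there were no strata still contains it. If the strata predict the outcome, the standard error is too large and the confidence interval too wide. In a non-inferiority trial an acceptable valve would then miss the margin more often than it need.

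The strata here could well be prognostic. Protocol 5.1 admits high-risk patients at an STS score of at least 8% or a predicted operative mortality of at least 15%, and extreme-risk patients at a probability of death or serious irreversible morbidity above 50%. Access route follows from the state of the iliofemoral vessels, and major vascular complications are part of the safety composite.

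Set beside a stratified design, the words about combined cohorts and pooled access data look like a decision to drop the strata. The only comparison methods still legible, chi-square or Fisher's exact test in SAP 2.2.2 and the log-rank test in SAP 2.2.3, do not mention strata either.

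**Working it through.** **What the pooling sentence settles**

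Two choices are separate: which patients are analysed, and how the estimate and its variance are formed. SAP 2.3.1 settles the first: one test over all randomised patients, instead of one per risk cohort or access route. This agrees with SAP 2.4, which powers the combined cohort. It leaves the second open. A Mantel-Haenszel or stratum-weighted risk difference is also computed on the combined cohort with both access routes in it, so adopting one would not require the sentence to change. The chi-square, Fisher and log-rank lines stand under headings for descriptive statistics and are not tied to the primary non-inferiority test.

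**Size if the test did ignore the strata**

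*The plan's own figure.* The total of 750 cannot be reproduced, because alpha, margin and event rates are redacted. Assuming one-sided 0.025, 80% power, 375 per arm, no true difference and no dropout, margin = (1.960 + 0.842) × √(2p(1−p)/375). This is 6.1 points at an event rate of 10% and 10.0 points at 40%. The figure can be neither confirmed nor refuted.

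*Inputs.* 375 per arm (750 at 1:1). Stratum shares w and event rates p are assumptions, because no stratum rates are legible. Rates are equal in the two arms, and the arms are balanced exactly within strata.

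*Formulas.*
- Overall rate: p̄ = Σwp
- Variance ratio: R = Σwp(1−p) / [p̄(1−p̄)]
- Unstratified SE: U = √(2p̄(1−p̄)/375); stratified SE: S = U√R
- Margin giving a nominal 80%: M = (1.960 + 0.842)U
- Power of the unstratified test: Φ((M − 1.960U)/S)
- Power of the stratified test: Φ(M/S − 1.960)
- Type I error of the unstratified test: 1 − Φ(1.960U/S)
- Patients' worth of information: 750/R − 750

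*Modest case: rates 15% and 25%, shares 50:50.* p̄ = 0.20. R = (0.5×0.1275 + 0.5×0.1875)/0.16 = 0.1575/0.16 = 0.9844. U = 0.02921, S = 0.02898, so the SE is 0.79% too large. M = 0.0818. Power is 80.2% unstratified and 80.6% stratified.

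*Wide case: rates 10/20/30/45%, shares 40/10/40/10%.* p̄ = 0.225. R = (0.036 + 0.016 + 0.084 + 0.02475)/0.174375 = 0.16075/0.174375 = 0.9219. U = 0.03050, S = 0.02928, so the SE is 4.15% too large. M = 0.0854. Power is 81.0% unstratified and 83.1% stratified.

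| Assumed stratum rates (shares) | R | SE too large by | Power, unstratified | Power, stratified | Type I error, unstratified | Patients' worth |
|---|---|---|---|---|---|---|
| 20/20% (50:50) | 1.0000 | 0.0% | 80.0% | 80.0% | 0.0250 | 0 |
| 15/25% (80:20) | 0.9887 | 0.6% | 80.1% | 80.5% | 0.0244 | 9 |
| 15/20/22/30% (55:10:30:5) | 0.9885 | 0.6% | 80.1% | 80.5% | 0.0243 | 9 |
| 15/25% (50:50) | 0.9844 | 0.8% | 80.2% | 80.6% | 0.0241 | 12 |
| 10/30% (50:50) | 0.9375 | 3.3% | 80.8% | 82.5% | 0.0215 | 50 |
| 10/20/30/45% (40:10:40:10) | 0.9219 | 4.2% | 81.0% | 83.1% | 0.0206 | 64 |
| 10/40% (50:50) | 0.8800 | 6.6% | 81.5% | 84.8% | 0.0183 | 102 |

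Before rounding, the gaps in power are 80.45 − 80.13 = 0.3, 80.45 − 80.14 = 0.3 and 80.61 − 80.19 = 0.4 points in the three modest rows, and 82.47 − 80.76 = 1.7, 83.10 − 80.96 = 2.1 and 84.77 − 81.52 = 3.3 points in the three wide rows. In every row the unstratified test has at least 80% power and a type I error no higher than 0.025.

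**The case for a change.** The strongest reply is that no legible sentence carries the strata into the primary analysis, every legible comparison method is unstratified, and stratifying costs no patients. SAP 2.6 requires all primary endpoints to be met, so small losses compound: if both endpoints behaved like the widest four-stratum case and were independent, joint power would be 0.810² = 65.6% unstratified against 0.831² = 69.1% stratified. The superiority tests named in SAP 2.11 would carry the same standard error.

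The principle stands: after stratified allocation, a variance that respects the strata is the better choice when they are prognostic. The step from that principle to a fault in this plan does not. The sections where the strata would appear are the ones blacked out, so their silence is no evidence. The joint-power figure also depends on wide stratum rates that the documents do not show. The surgical-risk thresholds in Protocol 5.1 predict the outcome of open surgery, not the event rates after transcatheter replacement that enter the formula.

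A further worry is that withdrawals might fall unevenly across strata. The primary analysis is ITT, and the additional analyses of both primary endpoints listed as Protocol 11.7.2 and 11.7.3 are redacted, so a lack of protection cannot be asserted.

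**Conclusion.** The concern does not hold. The plan commits to one overall test on all randomised patients, which is consistent with its power statement and compatible with a stratified estimate and variance. Nothing legible says that the primary test ignores the strata, so an inflated standard error cannot be stated as fact.

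If the test were unstratified, the error would be conservative. Type I error would lie between 0.0183 and 0.0250, and power between 80.0% and 81.5% against a plan of at least 80%. The forgone gain would be 0.3 to 0.4 power points for stratum spreads of 10 to 15 points, and 1.7 to 3.3 points only for spreads of 20 to 35 points. No primary conclusion would become invalid. These sizes rest on assumed stratum rates and shares, one-sided 0.025, exact balance within strata, no true difference and a margin set for 80% power. Whether the redacted method is in fact stratified remains unknown from the public documents.

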2.3.2 Primary Endpoint (FlexNav cohort)

Acceptable safety of the FlexNav™ Delivery System will be determined from a predefined precision estimate for VARC II-defined major vascular complications at 30 days. Results will be summarized and descriptively compared in context of results for the first-generation Delivery System in the randomized cohort (Portico arm) of the pivotal IDE trial.

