## 2.3 Rationale (Pivotal IDE and CAP)

### 2.3.1 Pivotal IDE Rationale

The rationale for this study is to potentially offer a SJM transcatheter Portico valve that is safe and effective for subjects with symptomatic, severe aortic valve stenosis who are considered at high or extreme risk for conventional surgical aortic valve replacement.

The rationale for conducting the FlexNav study as a separate arm of the pivotal IDE trial is to enable the direct comparison of 30-day safety outcomes data for the FlexNav™ Delivery System to the first-generation Portico Delivery System. Results from the FlexNav study will be included in a PMA application to support US approval of the Portico Transcatheter Heart Valve and FlexNav™ Delivery System.

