#### 1.2 Study Design and Objectives

The primary objective of the PORTICO pivotal IDE FlexNav study (“FlexNav study”) is to characterize the safety of the second-generation FlexNav™ Delivery System (“FlexNav™ Delivery System”).

The FlexNav study will be conducted as a prospective, multicenter, investigational study arm of the PORTICO pivotal IDE trial. Up to 200 patients (includes a maximum of 100 roll-ins) with symptomatic, severe aortic stenosis considered by a local Heart Team to be high or extreme risk for surgical aortic valve implantation will be enrolled from up to 70 US and Australian IDE sites. Upon provision of informed consent, subjects will undergo Portico valve implantation via a transfemoral or alternative access approach. Subject selection and key data collection will follow the pivotal IDE protocol to facilitate direct comparison of safety outcomes with the randomized cohort.

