## 6.2 Roll-in Cohort

A minimum of one (1) and up to three (3) roll-in subjects will be required per primary implanting physician at each site. Data from roll-in subjects will be added to the IDE Roll-in Registry and will not be included in the analysis population of 100 subjects. A maximum of 100 roll-in subjects will be permitted in the study.

The total number of roll-in subjects required per site will be at the discretion of the Sponsor and will be based on the primary implanting physician's recent Portico implant experience.

[REDACTED]

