### 10.4 Descriptive Endpoints

Descriptive endpoints will be summarized and presented for the analysis population (n=100 subjects) and according to access route (transfemoral vs alternative access). Additionally, all descriptive endpoints at 30 days will be summarized and descriptively compared to rates reported in the randomized cohort of the pivotal IDE trial as well as published results for Portico and latest-generation commercially available valves.

[Redacted]

[Redacted]

[Redacted]

[Redacted]

[Redacted]

[Redacted]

[Redacted]

[Redacted]

[Redacted]

[Redacted]

[Redacted]

[Redacted]

[Redacted]

[Redacted text block]

[Redacted text block]

[Redacted text block]

[Redacted text block]

[Redacted text block]

[Redacted text block]

[Redacted text block]

[Redacted text block]

[Redacted text block]

[REDACTED]

[REDACTED]

[REDACTED]

[REDACTED]

[REDACTED]

[REDACTED]

[REDACTED]

[REDACTED]

[REDACTED]

[REDACTED]

[REDACTED]

[REDACTED]

[REDACTED]

[REDACTED]

[REDACTED]

[REDACTED]

[REDACTED]

[REDACTED]

[REDACTED]

[REDACTED]

[REDACTED]

[REDACTED]

[REDACTED]

[REDACTED]

[REDACTED]

[REDACTED]

[figure not shown]
[figure not shown]
[Redacted text block]

[Redacted text block]

[Redacted text block]

[Redacted text block]

[Redacted text block]

[Redacted text block]

[Redacted text block]

[Redacted text block]

[Redacted text block]

[Redacted text block]

[REDACTED]

[REDACTED]

[REDACTED]

[REDACTED]

[REDACTED]

[REDACTED]

[REDACTED]

[REDACTED]

[REDACTED]

[REDACTED]

[REDACTED]

[REDACTED]

[REDACTED]

[REDACTED]

[REDACTED]

[REDACTED]

[REDACTED]

[REDACTED]

[REDACTED]

[REDACTED]

[REDACTED]

[REDACTED]

[REDACTED]

[REDACTED]

[REDACTED]

[REDACTED]

[REDACTED]

[REDACTED]

[REDACTED]

[REDACTED]

[REDACTED]

[REDACTED]

[REDACTED]

[REDACTED]

[REDACTED]

[REDACTED]

[REDACTED]

[REDACTED]

[Redacted text block]

[Redacted text block]

[Redacted text block]

[Redacted text block]

[Redacted text block]

[Redacted text block]

[Redacted text block]

[Redacted text block]

[Redacted text block]

[Redacted text block]

[Redacted text block]

[Redacted text block]

[Redacted text block]

[Redacted text block]

[Redacted text block]

[Redacted text block]

[Redacted text block]

[Redacted text block]

[Redacted text block]

[REDACTED]

[REDACTED]

[REDACTED]

[REDACTED]

[REDACTED]

[REDACTED]

[REDACTED]

[REDACTED]

[REDACTED]

[REDACTED]

[REDACTED]

[REDACTED]

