2.2 Statistical Methods

2.2.1 Descriptive Statistics for Continuous Variables

For continuous variables, results will be summarized with the numbers of observations, means, and standard deviations, and in addition, with medians, quartiles, minimums, maximums, and 95% confidence intervals for the means, when specified.

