2.2.2 Descriptive Statistics for Categorical Variables

For categorical variables, results will be reported as frequencies with percentages and were compared using chi-square tests or two-tailed Fisher's exact test.

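### Does resting acceptable FlexNav safety on a predefined precision estimate leave the FlexNav arm without a usable criterion?

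*SAP*

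**What the plan says.** SAP 2.3.2 and Protocol Appendix W, 10.3, share one sentence: acceptable safety of the FlexNav delivery system "will be determined from a predefined precision estimate for VARC II-defined major vascular complications at 30 days". Both then say that results will be compared descriptively with the first-generation system in the Portico arm of the randomized cohort.

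The stated aim is modest. The SAP's objective reads "The objective of the FlexNav study is to characterize the safety of the second-generation Portico Delivery System". Comparison is nevertheless part of the arm's purpose: Protocol 2.3.1 gives the reason for a separate arm as "to enable the direct comparison of 30-day safety outcomes data for the FlexNav" system against its predecessor, and Appendix W, 1.2, aligns subject selection and data collection "to facilitate direct comparison of safety outcomes with the randomized cohort".

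On reporting, SAP 2.2.1 offers "95% confidence intervals for the means, when specified" for continuous variables. SAP 2.2.2 says "For categorical variables, results will be reported as frequencies with percentages", with chi-square or Fisher tests. Appendix W, 10.4, has descriptive endpoints "summarized and presented for the analysis population (n=100 subjects) and according to access route". Roll-in subjects "will not be included in the analysis population of 100 subjects" (Appendix W, 6.2).

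**The concern.** Precision and acceptability are different properties. A confidence interval can be narrow around a bad rate. A rule that looks only at width limits the rate indirectly, through the link between a proportion and its variance, and the visible sentence gives neither the width nor the interval method.

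The second worry is the comparison with the first-generation system. It is a stated purpose of the arm, yet the visible text attaches no interval to the difference, and the general rules for categorical data mention none. A bare difference of a few points between 100 subjects and the Portico arm could be over-read in either direction.

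This is the arm's only primary endpoint, and its 30-day data support the marketing application. A reader of that application would want to know whether acceptable safety refers to the size of the rate or to the width of its interval.

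**Working it through.** **Inputs.** FlexNav analysis n = 100 (SAP 1.3; Appendix W, 6.2 and 10.4). Randomized cohort of 750 at 1:1 (SAP 1.3 and 1.5), so 750/2 = 375 in the Portico arm. No expected rate, width, limit or confidence level is visible for FlexNav, so the 100 cannot be reproduced. All rates and widths below are assumptions, with a 95% level.

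**If the criterion were an interval width.** The Wald half-width is 1.96 × √(p(1−p)/100). At 6 events it is 1.96 × √(0.06 × 0.94/100) = 4.7 points; at 7 events it is just over 5.0. A 5-point limit therefore passes up to 6 events. The same search with half the Clopper-Pearson width gives the other event column. The last two columns are binomial probabilities of passing when n = 100 and the true rate is 15%.

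| Half-width limit | Most events passing, Wald | Most events passing, exact | Pass probability, Wald | Pass probability, exact |
|---|---|---|---|---|
| 5 points | 6 | 5 | 0.5% | 0.2% |
| 6 points | 10 | 8 | 9.9% | 2.8% |
| 7 points | 15 | 12 | 57% | 25% |
| 8 points | 21 | 18 | 96% | 84% |

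The half-width is largest at p = 50%: 1.96 × √(0.25/100) = 9.8 points. A Wald limit of 10 points would be met whatever the rate. So a tight width does screen out high rates, and a loose one does not.

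**If the criterion were an upper confidence limit against a rate.** This would be an ordinary single-arm rule. Exact 95% intervals at 5, 10 and 15 events of 100 are 1.6–11.3%, 4.9–17.6% and 8.6–23.5%. The method would be sound and only the term would be loose.

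**Which case applies.** The documents as released do not say. The word predefined points to a definition elsewhere. Protocol 11.10, which covers FlexNav statistics, is redacted. The visible Appendix W passes from 9.1 to 10.3, so 10.1 and 10.2, immediately before the sentence, cannot be read. Text after SAP 2.4.3 is also blacked out.

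**The comparison.** With the same rate p in both groups, the half-width of the difference is 1.96 × √(p(1−p)(1/100 + 1/375)):

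- p = 5%: ±4.8 points
- p = 10%: ±6.6 points
- p = 15%: ±7.9 points

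If 350 of the Portico arm (an assumed number) had an attempted implant, these become ±4.8, ±6.7 and ±7.9. The 375 takes the whole arm as first-generation, although Protocol 1.2.1 moves all active arms to FlexNav from version L.

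**The case for a change.** The strongest case for a change is that the two sentences are fully visible and fall short under either reading. If the criterion is a confidence limit, precision estimate misnames it. If it is a width, it does not measure acceptability. Either way an edit in two places, using data already collected, would help the reader. The visible reporting rules also promise no interval for a proportion or a difference, although comparison is why the arm exists.

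The naming point stands: the sentence is loosely worded and does not say where the criterion is defined. The rest does not carry. Under the first reading the method is sound, and a reader of the unredacted plan may find the definition immediately before the sentence in Appendix W. The second reading is a guess about hidden text, and its consequences run from under 1% to 96% depending on a width nobody outside the sponsor can see.

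A precision estimate of a rate is ordinarily its confidence interval, so an interval for the FlexNav rate is probably already planned. SAP 2.2.1 and 2.2.2 are general rules and do not exclude intervals for particular endpoints. An interval for the difference would be a reasonable courtesy, but it would show sampling error only. It would say nothing about the bias of a non-randomized comparison, and anyone can compute it from the reported counts and denominators. Intervals by access route would add little: with 10 alternative-access subjects and no events, the exact upper 95% limit is still 30.8%.

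**Conclusion.** No change follows. The wording is unclear about what the predefined quantity is, but no visible rule is shown to give a wrong answer and no stated figure is shown to be wrong. The plan cannot be said to lack a criterion, because the sections that would hold one are redacted or missing from view.

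The practical consequence is small. The arm is meant to describe safety, the first-generation comparison is declared descriptive, and no visible hypothesis test or error rate depends on the sentence. The 30-day rate in 100 subjects will be reported, and an analyst would naturally give it with an interval (for example 4.9–17.6% at 10 events). Naming the criterion more precisely would help the reader but would alter no result.

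This conclusion assumes that the predefined criterion does exist in the hidden text, as the sentence says. If that text showed a loose interval width serving as the sole test of acceptability, the methodological objection would become real; the documents as released do not establish it.
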